***** **Follow-up for Survival:** When a patient has either progressed or started a new anti-cancer treatment, the follow period up for overall survival (FU-OS) starts. FU-OS ends when the patient dies, is lost to follow up or withdraws consent for collection of overall survival data (see [Section 6.2.3.3](#)). These visits can be conducted as phone calls.

- a x is the number of the treatment cycle
- b x is the number of the follow-up visit starting with FU2-PD
- c x is the number of the follow-up survival assessment

- 1 Written informed consent must be obtained before any protocol-specific screening assessments are performed. Informed Consent must include consent to collection of demographic data. Re-consenting may become necessary when new relevant information becomes available and should be conducted according to the Sponsor's instructions.
- 2 Archival tumour tissue (either tissue block or 20 slides) to be provided (preferably from the time point closest to trial entry) at SV for retrospective analysis of HR/HER2 at the central laboratory. Results from central laboratory are not required prior to randomisation. Bone biopsy samples are not acceptable (see [Section 5.4.1](#)).
- 3 Full physical examination ([Section 5.2.1](#)): Cardiopulmonary examination, clinical tumour assessment, examination of regional lymph nodes and the abdomen, assessment of mental and neurological status. Post baseline: Additional symptoms which were not previously reported should be clarified. Includes height (only at SV) and weight.
- 4 Limited physical examination ([Section 5.2.1](#)): Cardiopulmonary examination, clinical tumour assessment, examination of regional lymph nodes and the abdomen. Includes weight.
- 5 Vital signs include respiratory rate, pulse, temperature and blood pressure
- 6 PRO questionnaires will be completed by the patient as their first activity when attending a study visit at the visits indicated in the [flow chart](#).
- 7 12-lead resting electrocardiograms (ECG) are recorded locally. ECG will be performed at SV and EOT, and if clinically indicated.
- 8 Echocardiography or MUGA will be performed at SV and EOT, and if clinically indicated. LVEF assessment does not need to be repeated during screening if there is valid result available from an assessment which was performed as part of routine clinical practice within 28 days prior to start of trial treatment.

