- 17 A blood sample from which the plasma needs to be separated and isolated within approx. 4 hours after blood collection. Plasma will be used for cfDNA isolation and further molecular analysis as described in [Section 5.4](#). Sample collection has to be performed (pre-dose) at baseline on C1V1, C3V1, EoT and at time of disease progression during FU-PD if applicable (Appendix 10.1).
- 18 Samples for bone remodelling markers in blood and urine will be taken (pre-dose) at C1V1, C2V3, C4V1, and EoT as described in [Appendix 10.1](#). Subsequent specimens for comparison should be collected at the same time of day as C1V1 sample. Urine samples must be provided by patient using second morning void (note: this may occur at home)
- 19 After the EOR/FU1 visit, only drug-related SAEs and AESIs need to be reported. For details refer to [Section 5.2.6.2](#).
- 20 Analgesic intake will be assessed and completed using Analgesic Quantification Algorithm (AQA) as part of concomitant medications assessment. During FU-PD only concomitant medications for treatment of a drug-related SAE or AESI will be recorded in the CRF.
- 21 Collection of information on progression, further anti-cancer treatment, pregnancy (if applicable – see footnote 25) and death. Information should be collected from the patient notes or by telephone contact with the patient. A formal study visit is not required.
- 22 In the case that prior information regarding the patient's genomic breast cancer signature is available, an anonymized copy of the report will be collected for the trial database and results will also be recorded in the CRF.
- 23 Information on caregiver support (home care), general practitioner, outpatient and hospital visits (other than scheduled visits) will be collected in the CRF and as part of AE reporting to inform on healthcare resource use required. For details refer to [section 5.6.3](#).
- 24 Everolimus and exemestane should be taken once a day at approximately the same time of day, following a meal. The tablets may be taken at home or in the clinic.
- 25 Pre-menopausal women:

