4.2.1.3 Concomitant treatments

Symptomatic treatments of tumour-associated symptoms are allowed. Concomitant medications or therapy to provide adequate supportive care may be given as clinically necessary.

After study enrolment, palliative radiotherapy is not allowed (see also [Section 3.3.4.1](#)).

See [Section 4.4.1.1](#) for recommendations on supportive treatments whilst on trial treatment.

Premenopausal women must be treated with concomitant ovarian suppression with GnRH agonists, e.g. goserelin acetate. Estradiol and FSH need to be in the postmenopausal range on ovarian suppression at the time of screening, and monitoring of estradiol to document that it remains in the postmenopausal range during trial treatment is mandatory. If the estradiol level increases above the postmenopausal range during treatment a repeat test should be performed within 4 weeks. If still outside of desired range see [Section 3.3.4.1](#).

Use of denosumab for symptomatic treatment of skeletal-related events in adults with bone metastases (see [Section 4.2.2.1](#)) and/or bisphosphonate therapy for the treatment of osteoporosis are permitted during the study according to guidelines and as per SmPC/PI. If bisphosphonate/denosumab therapy is initiated after enrolment, the reason for its use must be clearly documented in the CRF and progression of disease must be excluded.

All medications (other than study drugs), including anaesthetic agents, vitamins, homeopathic/herbal remedies, nutritional supplements starting from the date of signature of informed consent and ending at the EOR/FU1 visit must be listed on the concomitant medication page of CRF including trade name, start and end dates, indication for use etc. as specified in the [Flow Chart](#). Indicating “parenteral nutrition” or “anesthesia” without specifying details will be sufficient.

Hematopoietic growth factors should be reserved to cases of severe neutropenia and anemia as per the labelling of these agents following ASCO guidelines ([R16-1540](#)).

In case of major surgery no modifications for xentuzumab/placebo treatment are needed. For everolimus and exemestane please refer to current SmPC/PI

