5.6.2 Analgesics use

Pain palliation resulting from antitumor therapy provides direct evidence of treatment benefit when combined with evidence of antitumor activity ([R17-3501](#)). Intensification of pain palliation will be defined as a ≥ 2 -point increase in the 8-point Analgesic Quantification Algorithm (AQA, see [Table 5.6.2: 1](#)). AQA is a modification of the World Health Organization Analgesic Treatment Ladder that includes additional specificity for patients receiving strong opioids. This algorithm facilitates differentiation between the full ranges of doses of strong opioids used by patients and thus, more accurately enables researchers to determine and control for changes in levels of analgesic medication use over time in clinical trials ([R17-2771](#)). It will be completed by the investigator at the same visits as the PROs.

Table 5.6.2: 1 AQA

AQA score	Description
0	No analgesic
1	Non-opioid analgesics
2	Weak opioids
3	Strong opioids ≤75 mg OME per day
4	Strong opioids >75–150 mg OME per day
5	Strong opioids >150–300 mg OME per day
6	Strong opioids >300–600 mg OME per day
7	Strong opioids >600 mg OME per day

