6.2.3.1 Extended follow-up period

For patients without objective disease progression and who have not started a new anti-cancer therapy prior to FU1, additional follow-up visits for progression will be performed every 56 days (8 weeks) \pm 7 days after the EOT visit for patients who did not yet start cycle 20 and every 16 weeks (112 days) for patients who started cycle 20. The follow-up for progression period will end at the earliest if one of the following events is met:

- Lost to follow-up
- Disease progression
- Start of a new anti-cancer therapy
- Death
- End of whole trial as specified in [Section 8.6](#)

The following will be obtained and/or performed during the follow-up visits for progression.

- For each drug-related SAE/AESI, the investigator should provide the information with regard to concomitant medication and the medication administered to treat the adverse events on the appropriate CRF pages and the SAE form including trade name, indication and dates of administration
- Record performance status (ECOG)
- Quality of life questionnaires
- Perform tumour assessment and imaging
- Treatment and start date of any subsequent anti-cancer therapy including the name and type of the anti-cancer drug and/or best supportive care (if applicable)
- Outcome (in case the patient had PD the actual date of PD shall be recorded, date of and reason for death, if applicable)
- Results from pregnancy testing (if applicable) see [Flowchart](#)

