otherwise, a response will be derived. If a ≥ 2 point increase from baseline in the BPI-SF, Item 3 is observed but the AQA score is missing, it will be assumed that no decrease in analgesics use has taken place.

[figure not shown]
Table 5.2.2: 1 Derivation rules for pain progression or intensification of pain palliation

[figure not shown]
Status at time of analysis	Outcome	Date of outcome
No baseline assessment and/or no post-baseline assessments		
Death on or before the second planned assessment	Event*	Date of death
Vital status is unknown or alive or death after second planned assessment	Censored	Date of randomisation
With baseline and at least one post-baseline assessment		
Alive and event-free, no more than one consecutively missed assessment	Censored*	Date of last assessment
Alive and event-free, two or more consecutively missed assessments	Censored*	Date of last assessment prior to missed assessments
Alive with event, no more than one consecutively missed assessment prior to event	Event*	Date of assessment of event
Alive with event, two or more consecutively missed assessments prior to event	Censored*	Date of last assessment prior to missed assessments
Death and event-free, no more than one consecutively missed assessment prior to death	Event*	Date of death
Death and event-free, two or more consecutively missed assessments prior to death	Censored*	Date of last assessment prior to missed assessments
Initiation of subsequent anti-cancer therapy		
Subsequent anti-cancer therapy started before outcomes flagged with a ‘*’ above	Censored	Date of last assessment before subsequent anti-cancer therapy (or date of randomisation if none exist)

[figure not shown]
* For these outcomes if initiation of subsequent anti-cancer therapy occurred prior to the outcome date then the rule for the final row of table will be used instead

[figure not shown]

[figure not shown]

[figure not shown]

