In order to identify whether consecutive imaging time points are missing for a patient a nominal time point [8, 16, 24 weeks and every 8 weeks thereafter up to 80 weeks, and every 12 weeks thereafter] will be assigned to each image. This will be achieved by creating time windows for each assessment as detailed in [Table 6.7: 1](#) below. If a patient does not have an image in one of the time windows when one is expected they will be considered as having 'missed an assessment' for that time-point. In case a patient has more than one assessment in one window, the assessment with the latest outcome will be used for the analysis unless progressive disease (PD) has been recorded earlier then PD will be used. Additionally, if a patient has multiple imaging dates within an assessment (e.g. a different target lesion imaging date to the non-target lesion imaging date), if the overall response is PD the earliest imaging date will be used, otherwise the latest imaging date will be used. Note for the slotting of imaging data and the derivation of time to efficacy events in general, 'Day 1' will be considered as the day of randomisation.

Table 6.7: 1 Nominal time-points and windows for imaging

Nominal time-point [Weeks]	Nominal time-point [Days]	Window [Days]
0	1	<=1
8	57	[2, 85]
16	113	[86, 141]
+8 weeks*	+56 days*	[+56 days, +56 days]*
80	561	[534, 603]
92	645	[604, 687]
+12 weeks*	+ 84 days*	[+84 days, +84 days]*

* For subsequent visits, add value to previous record in respective column

In a similar fashion to imaging time points, missed PRO assessments will be identified as detailed in Table 6.7: 2.

Table 6.7: 2 Nominal time-points and windows for PROs

Nominal time-point [Weeks]	Nominal time-point [Days]	Window [Days]
0	1	<=1 [#]
4	29	[2, 43]
8	57	[44, 71]
+4 weeks*	+28 days*	[+28 days, +28 days]*
80	561	[548, 589]
88	617	[590, 645]
+8 weeks*	+56 days*	[+56 days, +56 days]*

* For subsequent visits, add value to previous record in respective column

[#] Note any Course 1, Visit 1 data recorded prior to starting study medication will be defaulted to Day 1 even if it was after the randomisation date

Note if a patient discontinues study treatment and enters the follow-up for progression then PRO assessments will follow the imaging assessment schedule, so will either be 8-weekly or 12-weekly dependent upon whether reached Week 80 (Cycle 20) or not.

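### The protocol contradicts itself on whether analgesic use (AQA) is recorded during follow-up for progression, and the SAP still treats a visit with a pain score alone as a complete assessment for the pain endpoint

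*Protocol*

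**What the plan says.** **Collection of analgesic data**
- Flow Chart, footnote 20: "Analgesic intake will be assessed and completed using Analgesic Quantification Algorithm (AQA) as part of concomitant medications assessment". The next sentence reads "During FU-PD only concomitant medications for treatment of a drug-related SAE or AESI will be recorded in the CRF". The concomitant-medication row at the FUx-PD visit carries this footnote, and the chart has no separate AQA row.
- Protocol 4.2.1.3: medications are recorded from consent, "ending at the EOR/FU1 visit must be listed on the concomitant medication page of CRF".
- Protocol 5.6.2, on the AQA: "It will be completed by the investigator at the same visits as the PROs".

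**Collection of pain scores**
- Footnote 6 of the Flow Chart sets the timing: "PRO questionnaires will be completed by the patient as their first activity when attending a study visit at the visits indicated in the" (the sentence ends by pointing to the chart). The questionnaire row is marked at EOT, EOR/FU1 and FUx-PD.
- Protocol 6.2.3.1 includes "Quality of life questionnaires" among the FU-PD procedures. It does not name the AQA.

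**Analysis**
- SAP 6.7: "if a patient discontinues study treatment and enters the follow-up for progression then PRO assessments will follow the imaging assessment schedule". The pain endpoint therefore keeps running in FU-PD.
- SAP 5.2.2 defines an event as a BPI-SF item 3 rise of at least 2 points without an AQA decrease of at least 1 point, or an AQA rise of at least 2 points, or death. A time-point is missed when there is no assessment for both instruments; otherwise a response is derived. When a BPI rise of at least 2 points "is observed but the AQA score is missing, it will be assumed that no decrease in analgesics use has taken place".

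**The concern.** The AQA component exists to count patients whose pain score stays level because their analgesia was stepped up. The BPI-SF cannot show that alone. The AQA also qualifies the BPI component, since a BPI rise counts only if analgesic use has not fallen. Both uses need an AQA score at each visit where the BPI-SF is completed.

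Footnote 20 and Section 4.2.1.3 point sites away from recording analgesics in FU-PD, while Section 5.6.2 points them towards it. A site could reasonably follow either. If it followed the footnote, the endpoint definition changes without notice after EOR/FU1: one of the two non-fatal components cannot be observed, the other loses its qualifier, and the SAP goes on treating the visits as complete. The SAP has a rule for a BPI rise with the AQA missing, but none for an AQA rise that was never recorded.

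**Working it through.** No sample size, power or alpha figure depends on this point, so the check is a comparison of passages.

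**Step 1: is the AQA collected in FU-PD?** Footnote 20 makes it part of a medication assessment that is restricted in FU-PD, and 4.2.1.3 stops the full listing at EOR/FU1. Section 5.6.2 ties it to the questionnaire visits, which include FU-PD. The text does not say which governs.

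**Step 2: when can a gap begin, and in whom?** Full medication recording runs to EOR/FU1, which is 42 (+7) days after all trial medication stops (Protocol 6.2.2.1). FU-PD ends at progression or the start of further anti-cancer treatment (Flow Chart notes). The gap is therefore confined to visits after EOR/FU1 in patients with neither.

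**Step 3: does a BPI-only visit count as assessed?** The SAP's phrase about having no assessment for both instruments could be read two ways. The sentence that follows settles it by deriving an outcome from a BPI rise with the AQA missing. A BPI-only visit is thus not a missed assessment, and the rule for two consecutive missed assessments in SAP Table 5.2.2: 1 is not triggered.

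**Step 4: compare outcomes at an FU-PD visit**, changes being from baseline:

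| True change | AQA recorded | AQA not recorded |
|---|---|---|
| BPI flat; AQA 0 to 3 (no analgesic to strong opioid, +3) | Event | No event; stays at risk |
| BPI +2; AQA down 1 | No event | Event by default |
| BPI +2; AQA unchanged | Event | Event |
| BPI flat; AQA flat | No event | No event |

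The first two rows go wrong in opposite directions, so the net effect cannot be signed from the documents. If 5.6.2 was followed, the middle column applies and no problem arises.

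**Step 5: size.** The documents give no count of FU-PD patients or pain events. For illustration only, assume that 10–20% of 80 patients enter FU-PD, 30–50% of those worsen there, and 30–50% of the worsenings show through the AQA:
- low: 80 × 0.10 × 0.3 × 0.3 = 0.7 events
- high: 80 × 0.20 × 0.5 × 0.5 = 4.0 events

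All three fractions are assumptions. The sum also treats each unseen AQA rise as lost for good, although a later BPI rise or death could still give an event.

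**The case against.** The strongest reply is that Section 5.6.2 is the body text on the AQA, is explicit, and makes no exception for FU-PD. On this view the restriction in footnote 20 concerns the medication entries in the CRF, and the footnote's AQA sentence has no visit limit of its own. Section 4.2.1.3 likewise concerns the medication page rather than the score. The absence of the AQA from 6.2.3.1 proves little, because that list also leaves out the limited physical examination, vital signs and health care resource use, all marked at FUx-PD in the Flow Chart. This stands to the extent that loss of data is possible, not certain. It does not remove the conflict.

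A reader might infer several stronger points that the documents do not support:

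- *Analgesic data are lost as soon as treatment stops.* Medications are recorded in full through EOR/FU1.
- *The AQA would be scored 0 from the shortened medication page, giving a false decrease that cancels a real BPI rise.* No passage derives the score from that page; the investigator completes it. When it is missing, the SAP assumes no decrease, so the BPI rise becomes an event.
- *Patients who stop for toxicity or symptomatic decline are generally carried as event-free.* The rationale in Global Amendment 4 foresees such patients starting further therapy before objective progression. They would then leave FU-PD and fall under the SAP's censoring rule for subsequent therapy.
- *The error differs between arms.* The documents give no discontinuation figures by arm, and the trial was double-blind when these data were collected.

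It is also fair to say that the affected group is likely to be limited, since Protocol 6.2.2.1 expects progression to be documented by EOR/FU1 in most patients.

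**Conclusion.** The contradiction is real, and the SAP does not absorb it. If footnote 20 was followed, then after EOR/FU1, in patients without progression or new anti-cancer therapy, AQA rises of 2 points or more go uncaptured, those patients remain at risk as event-free, and BPI rises of 2 points or more count as events without the analgesic qualifier. How often this happened depends on what sites did and cannot be read from the documents. The number of events is unknown and probably small.

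The consequence is limited. This is a secondary endpoint in a Phase II trial evaluated exploratively, with no formal hypothesis testing unless the trial is expanded, and the primary PFS analysis is untouched. The point still merits action, because the endpoint is analysed with the same methods as PFS and the remedy is cheap.

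**What to change.** **Protocol text.** Exempt analgesic intake and the AQA from the FU-PD limit in footnote 20 and from the EOR/FU1 cut-off in 4.2.1.3, and add the AQA to the list in 6.2.3.1. It is then scored at every FU-PD visit with a BPI-SF, as 5.6.2 already states. The cost is one item at visits that already take place.

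**Data already collected.** That Flow Chart is marked as no longer applicable, and questionnaire collection for ongoing patients stopped on 29 September 2021 (Protocol 5.6.1), so a text change cannot recover past scores. For the analysis:
1. Keep the current SAP 5.2.2 rule as the main analysis. Requiring both components there could turn consecutive BPI-only visits into missed assessments and discard observed BPI events and deaths.
2. Report, by arm, how many FU-PD visits have a BPI-SF item 3 score but no AQA.
3. Add a sensitivity analysis that censors at the last visit with both components.

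The cost is one count and one extra analysis. The sensitivity analysis will lose some later BPI events and deaths, which is why it should support the main result and not replace it.

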AE	Adverse Event
AESI	Adverse Event of Special Interest
AI	Aromatase inhibitor
AKT	Protein kinase B-alpha
ALT	Alanine amino transferase
AMP	Auxiliary medicinal product
ANC	Absolute neutrophil count
ANCOVA	Analysis of covariance
aPTT	Activated Partial Thromboplastin Time
AQA	Analgesic Quantification Algorithm
ASCO	American Society of Clinical Oncology
AST	Aspartate amino transferase
BI	Boehringer Ingelheim
BOLERO	Breast cancer trials of OraL EverOlimus
BPI-SF	Brief Pain Inventory– Short Form
BRS	Bone-only metastases randomized set
BUN	Blood urea nitrogen
C	Cycle x
CAP	College of American Pathologists
CCND1	Cyclin D1
CDK	Cyclin-dependent kinases
cf	Cell-free
CI	Confidence Interval
CPK	Creatine phosphokinase
C _{pre}	Pre-dose plasma concentration
CR	Complete response
CRA	Clinical Research Associate
CRF	Case Report Form
CRO	Contract research organisation
CT	Computed tomography
CTCAE	Common Terminology Criteria for Adverse Events
CTP	Clinical Trial Protocol
CTR	Clinical Trial Report
CYP	Cytochrome P450
DC	Disease control
DCR	Disease control rate
DILI	Drug Induced Liver Injury
DMC	Data Monitoring Committee
DNA	Deoxyribonucleic acid
ECG	Electrocardiography
ECOG	Eastern Cooperative Oncology Group
eDC	Electronic Data Capturing
e.g.	Exempli gratia (for example)
ELISA	Enzyme Linked Immunosorbent Assay

EOR	End of residual effect period
EOT	End of treatment
EQ-5D-5L	EuroQoL 5-dimension health status self-assessment questionnaire
ER	Estrogen receptor
EU	European Union
FDA	Food and Drug Administration
FDG-PET	Fluorodeoxyglucose positron-emission tomography
FFPE	Formalin fixed paraffin embedded
FGFR	Fibroblast growth factor receptor
FISH	Fluorescence in situ hybridisation
FSH	Follicle-stimulating hormone
FU	Follow-up
GCP	Good Clinical Practice
GGT	γ -glutamyltransferase
GMP	Good Manufacturing Practice
HbA1c	Glycated haemoglobin
HCRU	Health care resource utilisation
HDL	High-density lipoprotein
Hep	Hepatitis
HER2	Human epidermal growth factor receptor 2
Hgb	Haemoglobin
HIV	Human immunodeficiency virus
HR	Hazard ratio
HR	Hormone receptor
HRQOL	Health-related quality of life
IB	Investigator's Brochure
ICF	Informed consent form
ICH	International Council for Harmonisation
i.e.	Id est (that is)
IEC	Independent Ethics Committee
IGF	Insulin-like growth factor
IGF-1R	IGF1 receptor
IGFBP3	IGF-binding protein 3
IgG1	Immunoglobulin 1
IHC	Immunohistochemistry
ILD	Interstitial lung disease
IMP	Investigational medicinal product
INR	International Normalised Ratio
IR-A	Insulin receptor A
IRB	Institutional Review Board
IRT	Interactive Response Technology
ISF	Investigator Site File
i.v.	intravenous
Ki-67	Antigen KI67
KM	Kaplan-Meier
LDL	Low-density lipoprotein
LSLT	Last Subject Last Treatment
LSLVPE	Last Subject Last Visit Primary Endpoint

LSLVSE	Last Subject Last Visit Secondary Endpoint
LVEF	Left Ventricular Ejection Fraction
mAb	Monoclonal antibody
mBC	Metastatic breast cancer
MAPK	Mitogen-activated protein kinase
MedDRA	Medical Dictionary for Drug Regulatory Activities
MRI	Magnetic resonance imaging
mTOR	Mechanistic target of rapamycin
mTORC1	mTOR complex 1
MUGA	MUltiGated Acquisition scan
nAb	Neutralising antibody
NCI	National Cancer Institute
NE	Not evaluable
NFBSI-16	Network Functional Assessment of Cancer Therapy-Breast Cancer Symptom Index
NIMP	Non-investigational medicinal product
NSAID	Nonsteroidal anti-inflammatory drugs
NTX	N-terminal cross-linked telopeptide of type I collagen
NYHA	New York Heart Association
OME	Oral morphine equivalent
OPU	Operative Unit
OR	Objective response
ORR	Objective response rate
OS	Overall survival
p	Probability
P1NP	N-terminal propeptide of procollagen type 1
PFS	Progression-free survival
PgR	Progesterone receptor
PI3K	Phosphatidylinositol 3-kinase
PIK3CA	Phosphatidylinositol-4,5-bisphosphate 3-kinase catalytic subunit alpha
PD	Pharmacodynamics
PD	Progressive disease
PI	Prescribing information
PK	Pharmacokinetics
p.o.	Per os (oral)
PR	Partial response
PRO	Patient Reported Outcome
PTEN	Phosphatase and tensin homolog
Ras	Rat sarcome
RBC	Red blood cell
RECIST	Response Evaluation Criteria In Solid Tumors
REP	Residual Effect Period
RNA	Ribonucleic acid
RS	Randomised set
SAE	Serious Adverse Event
sAg	Surface antigen
SC	Steering Committee
SD	Stable disease

SmPC	Summary of Product Characteristics
SOP	Standard operating procedure
SS	Skeletal scintigraphy
SUSAR	Suspected Unexpected Serious Adverse Reactions
SV	Screening visit
TNM	Tumour-lymph nodes-metastases; classification of malignant tumours
T _{max}	Time from dosing to the maximum plasma concentration
TMF	Trial Master File
TS	Treated set
TSAP	Trial Statistical Analysis Plan
ULN	Upper limit of institutional normal
V	Visit
VAS	Visual analogue scale
VEGF-C	Vascular endothelial growth factor C
vs.	Versus
WBC	White blood cell
WHO	World Health Organization
XR	Radiography

